8.2. Events or outcomes not qualifying as adverse events or serious adverse events

8.2.1. Pregnancy

Female subjects who are pregnant or lactating at the time of vaccination must not receive additional doses of study vaccine but may continue other study procedures at the discretion of the investigator.

While pregnancy itself is not considered an AE or SAE, any adverse pregnancy outcome or complication or elective termination of a pregnancy for medical reasons will be recorded and reported as an AE or a SAE.

Note: The pregnancy itself should always be recorded on an electronic pregnancy report.

The following should always be considered as SAE and will be reported as described in Sections 8.4.1 and 8.4.3:

- Spontaneous pregnancy loss, including:
 - spontaneous abortion, (spontaneous pregnancy loss before/at 22 weeks of gestation)
 - ectopic and molar pregnancy
 - stillbirth (intrauterine death of foetus after 22 weeks of gestation).

Note: the 22 weeks cut-off in gestational age is based on WHO-ICD 10 noted in the EMA Guideline on pregnancy exposure [EMA, 2006]. It is recognized that national regulations might be different.

- Any early neonatal death (i.e. death of a live born infant occurring within the first 7 days of life).
- Any congenital anomaly or birth defect (as per [CDC MACDP] guidelines) identified in the offspring of a study subject (either during pregnancy, at birth or later) regardless of whether the foetus is delivered dead or alive. This includes anomalies identified by prenatal ultrasound, amniocentesis or examination of the products of conception after elective or spontaneous abortion.

Furthermore, any SAE occurring as a result of a post-study pregnancy AND considered by the investigator to be reasonably related to the investigational vaccine(s)/product(s) will be reported to GSK Biologicals as described in Section 8.4.3. While the investigator is not obligated to actively seek this information from former study participants, he/she may learn of a pregnancy through spontaneous reporting.

8.3. Detecting and recording adverse events, serious adverse events and pregnancies

8.3.1. Time period for detecting and recording adverse events, serious adverse events and pregnancies

All AEs starting within 30 days following administration of each dose of study vaccine must be recorded into the appropriate section of the eCRF, irrespective of intensity or whether or not they are considered vaccination-related.

The time period for collecting and recording SAEs will begin at the first receipt of study vaccine and will end at Month 14 (study end), i.e. at least 12 months following administration of the last dose of study vaccine for each subject. See Section 8.4 for instructions on reporting of SAEs.

All AEs/SAEs leading to withdrawal from the study will be collected and recorded from the time of the first receipt of study vaccine.

In addition to the above-mentioned reporting requirements and in order to fulfil international reporting obligations, SAEs that are related to study participation (i.e. protocol-mandated procedures, invasive tests, a change from existing therapy) or are related to a concurrent GSK medication/vaccine will be collected and recorded from the time the subject consents to participate in the study until she/he is discharged from the study.

The time period for collecting and recording pregnancies will begin at the first receipt of study vaccine and will end at Month 14 (study end), i.e. at least 12 months following administration of the last dose of study vaccine. See Section 8.4 for instructions on reporting of pregnancies.

The time period for collecting and recording of pIMDs will begin at the first receipt of study vaccine and will end at Month 14 (study end), i.e. at least 12 months following administration of the last dose of study vaccine. See Section 8.4 for instructions on reporting of pIMDs.

Intercurrent medical conditions (see Section 6.7) will be recorded until from Month 0 until Month 3. Intercurrent medical conditions will be recorded in AE/SAE screens as appropriate.

The occurrence of HZ will constitute an AE/SAE as appropriate. The occurrence of HZ is an intercurrent medical condition which should be reported until study end rather than Month 3. All other intercurrent medical conditions should be reported until Month 3.

An overview of the protocol-required reporting periods for AEs, SAEs, and pregnancies is given in Table 16.

CONFIDENTIAL

116796 (ZOSTER-033)
Protocol Amendment 2 Final

Table 16 Reporting periods for adverse events, serious adverse events, intercurrent medical conditions and pregnancies

Study activity	Dose 1 (Visit 1)	7 days Post Dose 1	30 days Post Dose 1		Dose 2 (Visit 2)	7 days Post Dose 2	30 days Post Dose 2		Phone contact Month 8	Phone contact Month 14 Study Conclusion
	Month 0				Month 2		Month 3		Month 8	Month 14
Timing of reporting	Day 0	Day 6	Day 29		Day 0	Day 6	Day 29			
Solicited AEs										
Unsolicited AEs										
AEs/SAEs leading to withdrawal from the study										
All SAEs ^a										
Potential immune-mediated diseases (pIMDs)										
Pregnancies										
Herpes Zoster (HZ) episodes (see Section 6.7)										
Intercurrent medical conditions (IMCs) excluding HZ (see Section 6.7)										

Note: For each solicited and unsolicited symptom the subject experiences, the subject will be asked if he/she received medical attention defined as hospitalisation, an emergency room visit or a visit to or from medical personnel (medical doctor) for any reason and this information will be recorded in the eCRF.

CONFIDENTIAL

116796 (ZOSTER-033)
Protocol Amendment 2 Final

^a SAEs related to study participation or GSK concomitant medication/vaccine are to be recorded from the time the subject consents to participate in the study. All other SAEs are to be reported after administration of the first dose of vaccine.

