3. STUDY DESIGN OVERVIEW

One arm (**HZ Group**), open (n = 96)

Visit 1 Month 0 Blood sampling* Vacc 1	Visit 2** Month 2 Vacc 2	Visit 3*** Month 3 Blood sampling*	Phone contact Month 8 (SFU)	Phone Contact Month 14 (SFU)
Follow-up period				

n = number of subjects

Vacc = vaccination

SFU = Safety follow-up

* Blood samples (approximately 8 mL) will be collected from all subjects at Visits 1 and 3 to assess humoral immune responses by a gE ELISA.

** The second dose of study vaccine will be administered 2 months after the first dose.

*** Visit 3 occurs approximately one month after the second vaccination.

Protocol waivers or exemptions are not allowed with the exception of immediate safety concerns. Therefore, adherence to the study design requirements, including those specified in the outline of study procedures (Section 5.6), are essential and required for study conduct.

- Experimental design: Phase III, non-randomised, open-label, multi-centre study with a single group.
- Duration of the study: Approximately 14 months. Each subject will be followed for approximately 12 months after the second vaccine dose for safety follow-up.
 - **Epoch 001:** Primary starting at Visit 1, Month 0 and ending at final safety follow up contact (i.e. 12 months following Dose 2).
- Study groups:

Table 1 Study group and epoch foreseen in the study

Study groups	Number of subjects	Age (Min/Max)	Epoch
			Epoch 001
HZ Group	96	≥ 50 YOA	x

Table 2 Study group and treatment foreseen in the study

Treatment name	Product name	Study Group
		HZGroup
HZ/su	VZV gE	x
	AS01 _B	

HZ/su = Herpes Zoster subunit vaccine; VZV = Varicella Zoster Virus; gE = recombinant purified Glycoprotein E; AS01_B = Adjuvant System AS01_B

- Control: historical control (results of this study will be compared with the ones of other HZ/su trials which include subjects without a history of HZ).
- Vaccination schedules: 0, 2 months

- Treatment allocation: Non-randomized. Subjects will be stratified by age: 50-59 YOA; 60-69 YOA and ≥ 70 YOA.
- Blinding: open-label (Table 3)

Table 3 Blinding of study epoch

Study Epochs	Blinding
Epoch 001	open

- Sampling schedule: Blood samples for humoral immunity (approximately 8 mL per visit) will be collected from all subjects at Visits 1 and 3.
- Type of study: self-contained.
- Data collection: Electronic Case Report Form (eCRF).

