^a Only for women of child-bearing potential. Refer to Section 5.7.6 for details.

^b Any subject with a clinically diagnosed HZ episode between Visit 1 and Visit 2 should **not** receive the second dose.

^c According to Section 6.7.

^d Study procedure to be assessed only after administration of vaccine after Visit 1.

Table 7 Intervals between study visits

Interval between visits	Optimal length of interval ¹	Allowed interval ² (range in days)
Visit 1 → Visit 2	2 months	49 - 83
Visit 2 → Visit 3	1 month	30 - 48
Visit 2 → Phone contact at Month 8	6 months	180 -240*
Visit 2 → Phone contact at Month 14	12 months	335 - 395 *

¹ Whenever possible the investigator should arrange study visits within this interval.

² Subjects will not be eligible for inclusion in one or more cohorts if they make the study visit outside this interval. Refer to Section 10.4 for the definition of the cohorts for analysis

* Intervals pertaining to phone contacts are only indicative and will not determine a subject's eligibility for inclusion for ATP analysis

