8.3.2. Post-Study adverse events and serious adverse events

A post-study AE/SAE is defined as any event that occurs outside of the AE/SAE reporting period defined in Table 16. Investigators are not obligated to actively seek AEs or SAEs in former study participants. However, if the investigator learns of any SAE at any time after a subject has been discharged from the study, and he/she considers the event reasonably related to the investigational vaccine/product, the investigator will promptly notify the Study Contact for Reporting SAEs.

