9. SUBJECT COMPLETION AND WITHDRAWAL

9.1. Subject completion

A subject who returns for the concluding visit/is available for the concluding contact foreseen in the protocol is considered to have completed the study.

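### The Month 14 call may be made from Day 335 after Dose 2, so the 12-month minimum safety collection stated in Section 8.3.1 is not guaranteed

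*Protocol*

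**What the plan says.** **Stated minimum.** Section 8.3.1 sets the end of SAE collection: it "will end at Month 14 (study end), i.e. at least 12 months following administration of the last dose of study vaccine for each subject". The next paragraphs end pregnancy and pIMD collection at the same point with the same 12-month minimum. Only the SAE sentence adds that this applies to each subject.

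**Permitted timing.** Table 7 (Section 5.6) gives 12 months as the optimal interval from Visit 2, the Dose 2 visit, to the Month 14 call, and 335 to 395 days as the allowed interval. Its footnote adds: "Intervals pertaining to phone contacts are only indicative and will not determine a subject's eligibility for inclusion for ATP analysis".

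**What ends follow-up.** Section 3 defines the single epoch as "Primary starting at Visit 1, Month 0 and ending at final safety follow up contact (i.e. 12 months following Dose 2"). Table 6 places Study Conclusion at that contact. Section 9.1 says: "A subject who returns for the concluding visit/is available for the concluding contact foreseen in the protocol is considered to have completed the study". For the time afterwards, Section 8.3.2 says: "Investigators are not obligated to actively seek AEs or SAEs in former study participants".

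**Design statement.** The synopsis and Section 3 use softer wording: "Each subject will be followed for approximately 12 months after the second vaccine dose for safety follow-up".

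**The concern.** A minimum and a window that opens before it cannot both describe the same follow-up. A site that calls a subject on Day 335 complies with Table 7, and the subject counts as a completer. Active collection then stops about a month before the point that Section 8.3.1 gives as the earliest end.

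The stake is the last month of the long-term safety data. The Amendment 1 rationale in Appendix C records that the Month 14 call was added, at a regulator's request, to extend safety follow-up to one year after the last vaccination. Section 10.5.1 counts vaccinated subjects with no reported event as event-free. A new event arising between an early call and Day 365 would therefore normally be analysed as no event. Anyone who takes Section 8.3.1 at its word would assume a full year of observation for every completer.

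**Working it through.** **Inputs**
- Stated minimum: 12 months after the last dose (Section 8.3.1), taken as 365 days.
- Allowed interval, Visit 2 to the Month 14 call: 335 to 395 days (Table 7).
- Planned enrolment: 96 (Section 4.1).

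**Step 1. Earliest allowed call, in months.** 335 / 30.4375 = 11.0 months. The latest, 395 / 30.4375, is 13.0 months. The window permits 11 to 13 months, so the stated minimum of 12 is not reproduced.

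**Step 2. Shortfall at the lower bound.** 365 − 335 = 30 days, or 30/365 = 8.2%. Counting twelve months of 30 days, it is 360 − 335 = 25 days. Neither convention removes the gap.

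**Step 3. Share of the window that falls short.** The midpoint is (335 + 395)/2 = 365, so the window is 365 ± 30 days. It contains 395 − 335 + 1 = 61 days. Days 335 to 364 (30 days) give less than 12 months, and Days 365 to 395 (31 days) meet it.

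**Step 4. Range of the total loss.** This takes all 96 subjects as receiving Dose 2 and being called within the window.
- All calls on Day 365 or later: zero.
- All calls on Day 335: 96 × 30 / 365.25 = 7.9 person-years.
- Calls spread evenly over the 61 days (for illustration; the protocol does not say this): 30/61 = 49% of subjects fall short. The mean shortfall over all subjects is (30 + 29 + … + 1)/61 = 465/61 = 7.6 days, and 96 × 7.6 / 365.25 = 2.0 person-years.

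**Step 5. Comparison with the other phone window.** The Month 8 call has a 6-month optimum and an allowed interval of 180 to 240 days. It opens at about six months (180/30.4375 = 5.9, or exactly 6 × 30) and runs later. Only the Month 14 window is centred on its target.

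**Step 6. Does another provision restore the minimum?** The footnote does not: it removes any consequence for the ATP cohorts and sets no firm earliest day. Section 8.3.2 does not: after study end it requires notification only of SAEs that the investigator happens to learn of and considers related.

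**The case against.** The strongest reply is that the protocol means approximately 12 months throughout. The synopsis and Section 3 say so, a 365 ± 30 day window fits that, and Table 7 asks investigators to keep to the 12-month optimum whenever possible. On this view Section 8.3.1 has merely worded the matter too firmly. That is a fair account of how the mismatch may have arisen, and it supports one of the two remedies. It does not reconcile the texts, because Section 8.3.1 still states a minimum three times.

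A reader might go further than the documents allow, in four ways.
- **That the plan cannot deliver 12 months.** Calls on Days 365 to 395 satisfy both sections. The minimum is unprotected, not unattainable.
- **That a secondary objective fails.** The second secondary objective (Section 2.2) and its endpoints (Section 10.2) run until study end and contain no 12-month minimum. They stay well defined after an early call.
- **That the annex report will claim 12 months for everyone.** Section 10.10.1 says only that an additional analysis will assess the safety follow-up.
- **That subjects are dropped after the call.** Known SAEs and pIMDs are followed until they resolve or stabilise (Section 8.5.1.2) and pregnancies to outcome (Section 8.5.2). What stops is the active search for new events.

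It also stands that the protocol gives no distribution of call dates and no event rate. The 7.9 person-years is therefore a bound for calls within the window, and no effect on any safety result can be shown.

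**Conclusion.** The point holds as a minor inconsistency in the current text. Section 8.3.1 states a 12-month minimum, and Table 7 allows the concluding call up to 30 days earlier. The loss lies between zero and about 7.9 person-years. The upper figure assumes that all 96 subjects receive Dose 2 and are called on the first allowed day, with 12 months taken as 365 days. Because the window is only indicative, a call before Day 335 is not barred either, so even 11 months is not a guaranteed floor.

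The effect is confined to the descriptive secondary safety period. The primary immunogenicity objective, the primary safety objective (which ends 30 days after the last vaccination), the sample size and the ATP cohorts do not depend on the timing of this call. A severity above minor is not supported.

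**What to change.** Reconcile Table 7 with Section 8.3.1 in one of two ways.

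1. **Preferred: protect the minimum.** Open the Month 14 window no earlier than Day 365 after Visit 2 (for example 365 to 395 days). Exempt that lower bound from the indicative-only footnote. State that Study Conclusion is not completed before that day for subjects still in follow-up. This keeps the one-year purpose recorded for Amendment 1. It costs a table cell and a sentence or two. With 365 to 395, the call window shrinks from 61 to 31 days; a later upper bound would avoid that but lengthen the study slightly. No visit, sample or subject is added.

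2. **Otherwise: correct the wording.** In the SAE, pregnancy and pIMD sentences of Section 8.3.1, replace the 12-month minimum with approximately 12 months, to match the synopsis and Section 3. This costs a few words but leaves some subjects with about 11 months. Changing the text to a minimum of 11 months would not work, because an indicative window does not guarantee that either.

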8.3.2. Post-Study adverse events and serious adverse events

A post-study AE/SAE is defined as any event that occurs outside of the AE/SAE reporting period defined in Table 16. Investigators are not obligated to actively seek AEs or SAEs in former study participants. However, if the investigator learns of any SAE at any time after a subject has been discharged from the study, and he/she considers the event reasonably related to the investigational vaccine/product, the investigator will promptly notify the Study Contact for Reporting SAEs.

8.3.3. Evaluation of adverse events and serious adverse events

8.3.3.1. Active questioning to detect adverse events and serious adverse events

As a consistent method of collecting AEs, the subject should be asked a non-leading question such as:

‘Have you felt different in any way since receiving the vaccine or since the previous visit?’

When an AE/SAE occurs, it is the responsibility of the investigator to review all documentation (e.g. hospital progress notes, laboratory and diagnostics reports) relative to the event. The investigator will then record all relevant information regarding an AE/SAE on the in the eCRF. The investigator is not allowed to send photocopies of the subject’s medical records to GSK Biologicals instead of appropriately completing the eCRF. However, there may be instances when copies of medical records for certain cases are requested by GSK Biologicals. In this instance, all subject identifiers will be blinded on the copies of the medical records prior to submission to GSK Biologicals.

The investigator will attempt to establish a diagnosis pertaining to the event based on signs, symptoms, and/or other clinical information. In such cases, the diagnosis should be documented as the AE/SAE and not the individual signs/symptoms.

8.3.3.2. Assessment of adverse events

8.3.3.2.1. Assessment of intensity

The intensity of the following solicited AEs will be assessed as described:

Table 17 Intensity scales for solicited symptoms in adults

Adverse Event	Intensity grade	Parameter
Pain at injection site	0	None
	1	Mild: Any pain neither interfering with nor preventing normal every day activities
	2	Moderate: Painful when limb is moved and interferes with every day activities
	3	Severe: Significant pain at rest. Prevents normal every day activities
Redness at injection site		Record greatest surface diameter in mm
Swelling at injection site		Record greatest surface diameter in mm
Fever*		Record temperature in °C/°F
Headache	0	Normal
	1	Mild: Headache that is easily tolerated
	2	Moderate: Headache that interferes with normal activity
	3	Severe: Headache that prevents normal activity
Fatigue	0	Normal
	1	Mild: Fatigue that is easily tolerated
	2	Moderate: Fatigue that interferes with normal activity
	3	Severe: Fatigue that prevents normal activity
Gastrointestinal symptoms (nausea, vomiting, diarrhoea and/or abdominal pain)	0	Gastrointestinal symptoms normal
	1	Mild: Gastrointestinal symptoms that are easily tolerated
	2	Moderate: Gastrointestinal symptoms that interfere with normal activity
	3	Severe: Gastrointestinal symptoms that prevent normal activity
Myalgia	0	Normal
	1	Mild: Myalgia that is easily tolerated
	2	Moderate: Myalgia that interferes with normal activity
	3	Severe: Myalgia that prevents normal activity
Shivering	0	None
	1	Shivering that is easily tolerated
	2	Shivering that interferes with normal activity
	3	Shivering that prevents normal activity

*Fever is defined as temperature $\geq 37.5^{\circ}\text{C}$ / 99.5°F for oral, axillary or tympanic route, or $\geq 38.0^{\circ}\text{C}$ / 100.4°F for rectal route. The preferred route for recording temperature in this study will be oral.

The maximum intensity of local injection site redness/swelling will be scored at GSK Biologicals as follows:

0	:	< 20 mm diameter
1	:	≥ 20 mm to ≤ 50 mm diameter
2	:	> 50 mm to ≤ 100 mm diameter
3	:	> 100 mm diameter

Temperature (measured by oral, axillary or tympanic route) will be scored at GSK Biologicals as follows:

0	:	< 37.5°C
1	:	37.5°C to 38.0°C
2	:	38.1°C to 39.0°C
3	:	> 39.0°

The investigator will assess the maximum intensity that occurred over the duration of the event for all unsolicited AEs (including SAEs) recorded during the study. The assessment will be based on the investigator's clinical judgement.

The intensity should be assigned to one of the following categories:

- 1 (mild) = An AE which is easily tolerated by the subject, causing minimal discomfort and not interfering with everyday activities.
- 2 (moderate) = An AE which is sufficiently discomforting to interfere with normal everyday activities.
- 3 (severe) = An AE which prevents normal, everyday activities (In adults, such an AE would, for example, prevent attendance at work and would necessitate the administration of corrective therapy.)

An AE that is assessed as Grade 3 (severe) should not be confused with a SAE. Grade 3 is a category used for rating the intensity of an event; and both AEs and SAEs can be assessed as Grade 3. An event is defined as 'serious' when it meets one of the pre-defined outcomes as described in Section 8.1.2.

8.3.3.2.2. Assessment of causality

The investigator is obligated to assess the relationship between investigational vaccine/product and the occurrence of each AE/SAE. The investigator will use clinical judgement to determine the relationship. Alternative plausible causes, such as natural history of the underlying diseases, concomitant therapy, other risk factors, and the temporal relationship of the event to the investigational vaccine/product will be considered and investigated. The investigator will also consult the IB to determine his/her assessment.

There may be situations when a SAE has occurred and the investigator has minimal information to include in the initial report to GSK Biologicals. However, it is very important that the investigator always makes an assessment of causality for every event prior to submission of the SAE report to GSK Biologicals. The investigator may change his/her opinion of causality in light of follow-up information and update the SAE information accordingly. The causality assessment is one of the criteria used when determining regulatory reporting requirements.

In case of concomitant administration of multiple vaccines, it may not be possible to determine the causal relationship of general AEs to the individual vaccines administered. The investigator should, therefore, assess whether the AE could be causally related to vaccination rather than to the individual vaccines.

All solicited local (injection site) reactions will be considered causally related to vaccination. Causality of all other AEs should be assessed by the investigator using the following question:

Is there a reasonable possibility that the AE may have been caused by the investigational vaccine/product?

- YES : There is a reasonable possibility that the vaccine(s) contributed to the AE.
- NO : There is no reasonable possibility that the AE is causally related to the administration of the study vaccine(s). There are other, more likely causes and administration of the study vaccine(s) is not suspected to have contributed to the AE.

If an event meets the criteria to be determined as 'serious' (see Section 8.1.2), additional examinations/tests will be performed by the investigator in order to determine ALL possible contributing factors for each SAE.

Possible contributing factors include:

- Medical history.
- Other medication.
- Protocol required procedure.
- Other procedure not required by the protocol.
- Lack of efficacy of the vaccine, if applicable.
- Erroneous administration.
- Other cause (specify).

